### **2.2.2 PDQ-39 Summary Index and Domain Scores**

Analysis Set:	Full Analysis Set
Analysis Variable(s):	PDQ-39 Summary Index PDQ-39 domain scores
Visit:	Baseline (prior to TVP-1012 administration), Week 14, Week 26, Week 40, Week 52, End of Treatment
Analysis Method(s):	The same analysis as 2.1.1.1 will be performed for the above analysis variables. However, the graphical display of the mean and standard deviation is excluded.

## **2.3 Statistical/Analytical Issues**

### **2.3.1 Adjustments for Covariates**

Not applied in this study.

### **2.3.2 Handling of Dropouts or Missing Data**

Missing test results and data determined to be non-evaluable according to the Handling Rules for Analysis Data and this statistical analysis plan will not be used for hypothesis testing and estimations. Values below/less than or equal to the lower limit of quantification will be treated as zero when calculating the descriptive statistics. Values above/greater than or equal to the upper limit of quantification will be treated as the upper limit of quantification when calculating the descriptive statistics.

### **2.3.3 Interim Analyses and Data Monitoring**

No interim analysis is planned.

### **2.3.4 Multicentre Studies**

Not applied in this study.

### **2.3.5 Multiple Comparison/Multiplicity**

Not applied in this study.

### 2.3.6 Use of an "Efficacy Subset" of Subject

Not applicable in this study.

### 2.3.7 Active-Control Studies Intended to Show Equivalence or Non-inferiority

Not applicable in this study.

### 2.3.8 Examination of Subgroups

#### 2.3.8.1 Examination of Subgroups for Secondary Endpoint

Analysis Set:	Full Analysis Set
Analysis Variable(s):	Change from baseline (prior to TVP-1012 administration) in the MDS-UPDRS Part II + Part III total score at end of treatment (at end of treatment-baseline (prior to TVP-1012 administration))
Subgroup(s):	Age (years) [Min<= - <65, 65<= - <=Max] Gender [Male, Female] Smoking history [Yes, No] Timing of Study Drug [Before breakfast, After breakfast] Administration Duration of Parkinson's disease (years) [Min<= - <1.5, 1.5<= - <=Max] Modified Hoehn and Yahr Scale [Min<= - <2.0, 2.0<= - <3.0, 3.0<= - <=Max]
Analysis Method(s):	Descriptive statistics and two-sided 95% confidence intervals of means will be provided for the above each subgroup by treatment group in the preceding study.

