6.2.3 Justification for Dose Regimen

[REDACTED]

In the preceding study, 1 mg of TVP-1012 or placebo was administered for 26 weeks to evaluate the efficacy and safety of TVP-1012 1 mg.

In this study, the dose of 1 mg of TVP-1012 will be maintained for subjects treated with 1 mg of TVP-1012 in the preceding study, to evaluate administration at 1 mg for 52 weeks. In addition, subjects treated with placebo in the preceding study will be switched to 1 mg of TVP-1012 in this study, to evaluate administration at 1 mg for 26 weeks, for the purpose of evaluating a large number of subjects as much as possible.

[REDACTED]

CONFIDENTIAL

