6.2.4 Justification for Treatment Period

Parkinson's disease is a progressive disease and long-term administration is anticipated when TVP-1012 is prescribed. Therefore, another 26-week extension of treatment was planned following the 26-week treatment in the preceding study to evaluate the long-term safety of TVP-1012 for 6 months and 12 months.

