13.3 Determination of Sample Size

Number of subjects to be enrolled in this study: approximately 182

[Justification of Sample size]

In the preceding study, the planned number of subjects to be randomized was a total of 240 (120 per group) and the planned number of subjects evaluable for the primary endpoint (change in the MDS-UPDRS Part II + Part III total score from baseline to Week 26 of the treatment period (LOCF)) was a total of 220 (110 per group).

Since this study is a long-term extension study in patients with early Parkinson's disease who have completed the 26-week treatment period in the preceding study, considering the potential dropouts in the preceding study, approximately 182 subjects will be enrolled in this study.

In addition, considering the potential dropouts in this study and in the preceding study, it is estimated that 155 subjects will be treated with 1 mg of TVP-1012 for 26 weeks and 59 subjects for 52 weeks.

CONFIDENTIAL

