## Glossary

- Descriptive statistics:

Number of subjects, mean, standard deviation, maximum, minimum, and quartiles

- MAV:

Markedly Abnormal Value

- Treatment groups in the preceding study:

TVP-1012 1 mg and placebo groups in the preceding study. However, they are shown as “1 mg ->1 mg group” and “P ->1 mg group” respectively in this statistical analysis plan.

- Study drugs for treatment period in both studies:

Study drug for treatment period in the previous study and study drug in this study

- Number of days after administration (days):

- A) For the analyses based on the data after administration of TVP-1012

The day before the day of first TVP-1012 administration is shown as Day -1 and the day of first TVP-1012 administration as Day 1. That is, shown as follows:

[If the treatment group in the preceding study is 1 mg ->1 mg group]

Day before the day of first study drug administration for the treatment period in the preceding study:	Day -1
Day of first study drug administration for the treatment period in the preceding study:	Day 1

[If the treatment group in the preceding study is P ->1 mg group]

Day before the day of first study drug administration in this study:	Day -1
Day of first study drug administration in this study:	Day 1

- B) For the analyses based on the data after study drug administration for the treatment period in the preceding study

The day before the day of the first study drug administration for the treatment period in the preceding study is shown as Day -1 and the day of the first study drug administration for the treatment period in the preceding study as Day 1.

- Number of days after the end of administration (days):

Day 1 is defined as the day following the later of “day of the last study drug administration for the treatment period in the preceding study” or the “day of the last study drug administration in this study.”

- Protocol Deviations:

Protocol deviations in this study, unless otherwise specified.

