### Definition of Visit Window

#### A) For the analyses based on the data after administration of TVP-1012

For each test, observation, and evaluation items, evaluable data (i.e., non-missing and acceptable according to the Handling Rules for Analysis Data) will be handled according to the following rules. However, the number of days after administration and number of days after the end of administration will be the contents of “For the analyses based on the data after administration of TVP-1012” in the Glossary.

Among the evaluation points, at points other than at the end of administration, evaluable data within the visit window will be used. If more than one evaluable data lies within the same visit window, the examinations, observation, and assessments with the Study Time closest to the scheduled Study Time will be used. If there are two observations equidistant to the scheduled Study Time, the later observation will be used. The size of difference from the Study Time will be determined based on the number of days after administration.

Among the evaluation points, at the end of administration, the data with the largest number of days after administration will be used among the evaluable data within the visit window.

MDS-UPDRS Part I, II, III, and IV Total Scores, MDS-UPDRS Part II + Part III Total Score, MDS-UPDRS Tremor, Muscle Rigidity, and Akinesia/Bradykinesia Scores, and MDS-UPDRS Individual Scores

Visit	Scheduled Study Time	Visit Windows	
		Number of days after administration	Number of days after the end of administration
Baseline (prior to TVP-1012 administration)	Number of days after administration: -1	-22 ~ -1	
Week 6	Number of days after administration: 42	1 ~ 55	< 8
Week 10	Number of days after administration: 70	56 ~ 83	< 8
Week 14	Number of days after administration: 98	84 ~ 118	< 8
Week 20	Number of days after administration: 140	119 ~ 160	< 8
Week 26	Number of days after administration: 182	161 ~ 202	< 8
Week 32	Number of days after administration: 224	203 ~ 237	< 8
Week 36	Number of days after administration: 252	238 ~ 265	< 8
Week 40	Number of days after administration: 280	266 ~ 300	< 8
Week 46	Number of days after administration: 322	301 ~ 342	< 8
Week 52	Number of days after administration: 364	343 ~ 385	< 8
At end of administration		1 ~ 385	< 8

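### The only efficacy subgroup table uses the last score on drug, so its subgroup differences can reflect time on drug and reason for leaving as well as response

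*SAP*

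**What the plan says.** SAP 2.3.8.1 takes as its one variable "Change from baseline (prior to TVP-1012 administration) in the MDS-UPDRS Part II + Part III total score at end of treatment". It covers six subgroup factors: age, gender, smoking history, timing of dose, duration of disease and modified Hoehn and Yahr stage. The method is "Descriptive statistics and two-sided 95% confidence intervals of means will be provided for the above each subgroup by treatment group in the preceding study". The only other subgroup section, SAP 3.1.3, concerns adverse events.

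The value is defined in part A of the SAP's visit-window section: "at the end of administration, the data with the largest number of days after administration will be used". For MDS-UPDRS the window is Days 1 to 385 and less than 8 days after the last dose. The window table labels this row as end of administration and the analysis sections say end of treatment; I read the two as the same.

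In the 1 mg → 1 mg group, Day 1 is the "day of first study drug administration for the treatment period in the preceding study", so the window runs across both studies. For the other group, Protocol 6.2.3 states that "subjects treated with placebo in the preceding study will be switched to 1 mg of TVP-1012 in this study, to evaluate administration at 1 mg". Their planned time on drug is 26 weeks, and Day 1 is the first dose in the extension.

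SAP 2.1.1.1 gives results at fixed visits, but only for the whole of each group. SAP 2.3.1 applies no covariate adjustment.

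**The concern.** The protocol bases the length of treatment on the fact that "Parkinson's disease is a progressive disease and long-term administration is anticipated when TVP-1012 is prescribed". If the score moves with time, a last-score variable measures different things in a subject who stopped at Week 10, one whose last score was at Week 26 and one who finished Week 52. Two subgroups with the same course over time would then show different means if their members stayed for different lengths of time or left for different reasons. Nothing in the table lets a reader separate this from a real difference in response. Exposure and completion are tabulated by treatment group (SAP 1.3.1 and 1.1.6) but not by subgroup. At stake is whether the table can be read as showing if efficacy varies with age, disease duration or stage.

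**Working it through.** **1. Planning figures.** Protocol 13.3 gives 240 randomised (120 per group) and about 182 entering the extension, and says "it is estimated that 155 subjects will be treated with 1 mg of TVP-1012 for 26 weeks and 59 subjects for 52 weeks". It states no dropout rates, so these figures cannot be derived from stated inputs. One assumed set reproduces them:

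- completers of the preceding study per group: 120 × 0.80 = 96
- entrants per group: 96 × 0.95 = 91.2, in total 182.4
- complete the extension, per group: 91.2 × 0.65 = 59.3
- on 1 mg for 26 weeks: 96 + 59.3 = 155.3

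The three rates are assumptions. Another set (24% dropout, all completers enter, 35% dropout) gives 182.4, 150.5 and 59.3, so the rates are not unique.

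**2. Share of Week 52 values in the 1 mg → 1 mg group.** Only this group can reach 52 weeks on drug, so all 59 belong to it. I treat them as the subjects with a Week 52 value.

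| Who is in the analysis set | Share with Week 52 value | Share earlier |
|---|---|---|
| All randomised to 1 mg | 59/120 = 49% | 51% |
| Planned evaluable number in the preceding study | 59/110 = 54% | 46% |
| Extension entrants only, 182/2 = 91 | 59/91 = 65% | 35% |

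In the last row every subject has completed Week 26, so the mix should run from about Week 26 to Week 52. In the first two rows it also includes earlier scores. In the P → 1 mg group the same mixing occurs over about 26 weeks.

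**3. Size of the artefact with no true subgroup difference.**

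Artefact = (difference in share reaching Week 52) × (mean change at Week 52 − mean change at the earlier last score).

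The inputs are assumed: gap 10 to 30 percentage points, drift 1 to 6 points.

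- smallest: 0.10 × 1 = 0.1 point
- middle: 0.20 × 3 = 0.6 point
- largest: 0.30 × 6 = 1.8 points

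If those who leave have worse last scores than the Week 52 completers by the same amounts, the results are the same with the sign reversed.

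**4. Sampling error for scale.** The 95% half-width of a difference between two equal subgroups is 1.96 × SD × √(2/n), with assumed SD 8 to 12 and n 30 to 60 per subgroup.

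- SD 8, n = 60: 1.96 × 8 × √(2/60) = 2.9 points
- SD 12, n = 30: 1.96 × 12 × √(2/30) = 6.1 points

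The largest assumed artefact, 1.8, is below the smallest half-width, 2.9.

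**5. Whether fixed visits are available.** In the 1 mg → 1 mg group, VISIT 8 (Days 175–189) falls in the SAP's Week 26 window (161–202) and VISIT 14 (Days 357–371) in the Week 52 window (343–385). In the P → 1 mg group dosing starts the day after VISIT 8, so the final visit falls between 357 − 189 = Day 168 and 371 − 175 = Day 196 on the TVP-1012 clock, which is inside the Week 26 window. Both fixed visits can be tabulated from planned data.

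**The case against.** The case against has several parts, and much of it stands.

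- **Direction.** A reader might infer that a subgroup whose members leave early will look better because its scores show less progression. The documents do not support this. Protocol 7.5 lists lack of efficacy as a reason for discontinuation, and Table 7.a excludes levodopa and dopamine agonists through VISIT 14. Subjects who worsen may therefore leave with poor last scores.
- **Who is pooled.** A reader might take it as fact that the variable includes subjects who never entered the extension. Protocol 13.1.1 leaves the definition of the full analysis set to the Handling Rules, which are not among the documents. Hence the 49% to 65% range.
- **Which subgroups.** Nothing in the documents shows that age, duration or stage affects how long a subject stays. It is a plausible expectation and no more.
- **Side-by-side columns.** SAP 2.3.8.1 asks for no difference between groups. The group contrast is in SAP 2.1.1.2, on a common clock, and unequal exposure is part of the design.
- **Fixed visits are also selective.** A Week 52 table keeps about 59 subjects and loses everyone who left. Week 26 in the 1 mg → 1 mg group comes from the preceding study and says little about long-term effect. End of treatment keeps most subjects and resembles the preceding study's LOCF endpoint. This argues against replacing it, but not against adding fixed visits beside it.
- **Weight.** The table is descriptive and without tests, on a secondary endpoint, and Protocol 13.1.3 plans no efficacy subgroup analysis.

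What remains is that the table mixes time points under any of these readings, and a confidence interval does not account for that.

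**Conclusion.** The point holds as a cheap improvement. The share of the 1 mg → 1 mg group with a pre-Week 52 value is about 35% to 51% on the planning figures, depending on the analysis-set definition and on equal entry from the two groups. Subgroup differences in this table can therefore carry time on drug and reason for leaving as well as response. The sign of any bias is unknown. The 0.1 to 1.8 point range rests wholly on assumed retention gaps and drift, and is probably smaller than the sampling error, which itself rests on assumed SDs and cell sizes. A reader might conclude that end of treatment is invalid and should be dropped or demoted; the selection at fixed visits means that does not follow. The primary safety endpoint is not affected.

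**What to change.** In SAP 2.3.8.1 keep end of treatment and add, by subgroup, the change from the pre-TVP-1012 baseline at:

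- Week 26 on the TVP-1012 clock (Days 161–202), for both groups
- Week 52 (Days 343–385), for the 1 mg → 1 mg group only

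Show median days on TVP-1012 for each subgroup beside the end-of-treatment row. The number of subjects needs no extra request, because it is already part of the SAP's descriptive statistics.

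No new data, visits or windows are needed. The cost is a larger table and fewer subjects per cell: on the planning figures about 91 to 96 of the 1 mg → 1 mg group at Week 26 and about 59 at Week 52. Fixed visits give every score in a cell the same nominal time on drug, but they do not remove the selection of those who stay. That selection is strongest at Week 52, and a footnote should say so.

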### 3 Safety Analysis

Of the safety evaluation variables in this study, the frequency of adverse events (AEs) will be used as the primary endpoint, and clinical laboratory test results, vital signs, ECGs, and weight will be used for the assessment of secondary endpoints.

#### 3.1 Treatment-Emergent Adverse Event

##### 3.1.1 Overview of Treatment-Emergent Adverse Events

Analysis Set: Safety Analysis Set

Analysis Variable(s): TEAEs that occurred after administration of TVP-1012

Categories: Relationship to Study Drug [Related, Not Related]  
Intensity [Mild, Moderate, Severe]

Analysis Method(s): The following summaries will be provided for each treatment group in the preceding study.

- (1) Overview of TEAEs
  - 1) All TEAEs (number of events, number and percentage of subjects)
  - 2) Relationship of TEAEs to study drug (number of events, number and percentage of subjects)
  - 3) Intensity of TEAEs (number of events, number and percentage of subjects)
  - 4) TEAEs leading to study drug discontinuation (number of events, number and percentage of subjects)
  - 5) Serious TEAEs (number of events, number and percentage of subjects)
  - 6) Relationship of serious TEAEs to study drug (number of events, number and percentage of subjects)
  - 7) Serious TEAEs leading to study drug discontinuation (number of events, number and percentage of subjects)
  - 8) TEAEs resulting in death (number of events, number and percentage of subjects)

TEAEs will be counted according to the rules below.

[Number of subjects with TEAEs]

- In case of “frequency distributions by relationship to study drug”  
A subject with occurrences of a TEAE in both categories (i.e., Related and Not Related) will be counted once in the Related category.
- In case of “frequency distributions by intensity”  
A subject with multiple occurrences of a TEAE will be counted once for the TEAE with the maximum intensity.
- In case of distributions other than the above  
A subject with multiple occurrences of a TEAE will be counted only once.

[Number of events]

For each summary, the total number of events will be calculated.

##### 3.1.2 Displays of Treatment-Emergent Adverse Events

Analysis Set: Safety Analysis Set

Analysis Variable(s):	TEAEs that occurred after administration of TVP-1012
Categories:	Intensity [Mild, Moderate, Severe] Time of Onset (days) [1<= - <84, 84<= - <168, 168<= - <252, 252<= - <336, 336<= - <=Max]
Analysis Method(s):	
The following summaries will be provided for each treatment group in the preceding study.
 
TEAEs will be coded using MedDRA and will be summarized using SOC and PT. SOC will be sorted alphabetically and PT will be sorted in decreasing frequency for tables provided by SOC and PT. SOC and PT will be sorted in decreasing frequency for tables provided by SOC only or PT only.
 
 
(1) All TEAEs by SOC and PT
 
(2) All TEAEs by SOC
 
(3) All TEAEs by PT
 
(4) Drug-Related TEAEs by SOC and PT
 
(5) Intensity of All TEAEs by SOC and PT
 
(6) Intensity of Drug-Related TEAEs by SOC and PT
 
(7) TEAEs Leading to Study Drug Discontinuation by SOC and PT
 
(8) Serious TEAEs by SOC and PT
 
(9) TEAEs by SOC and PT Over Time
 
 
The methods of counting events and calculating the percentage of subjects when conducting each frequency distribution will be as follows:
 
[Number of subjects with TEAEs]
 
 
• In case of “frequency distributions by SOC and PT, by SOC only, or PT only”
 
 
A subject with multiple occurrences of TEAE within a SOC will be counted only once in that SOC.
 
A subject with multiple occurrences of TEAE within a PT will be counted only once in that PT.
 
When calculating percentages for TEAE, the number of subjects in the safety analysis set will be used as the denominator.
 
 
• In case of “frequency distributions by SOC and PT”
 
 
A subject with multiple occurrences of a TEAE within a SOC or a PT will be counted only once for the TEAE with the maximum intensity.
 
When calculating percentages for TEAE, the number of subjects in the safety analysis set will be used as the denominator.
 
 
• In case of “frequency distributions by time of onset by SOC and PT”
 
 
For each time interval, a subject with multiple occurrences of TEAE within a SOC or a PT will be counted only once in that SOC or PT. When calculating the onset rate of TEAEs for each time interval, the number of subjects among the safety analysis set (i.e., subjects who either have an exposure or have an occurrence of a TEAE, during or after the corresponding time interval) will be used as the denominator and the number of subjects whose onset of any one of the TEAEs is within the time interval will be used as the numerator.

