10.1.8 Start Date

The date of onset of a PTE or an AE will be determined according to the following criteria.

PTE or AE	Date of onset
Signs, symptoms, and diseases (diagnoses)	The date on which the subject, the investigator or sub-investigator first noted the signs/symptoms of an AE.
Asymptomatic diseases	The date on which a definitive diagnosis is obtained through tests. The date on which a diagnosis is confirmed should be recorded, even when the test result indicates an old sign(s) of the disease, or an approximate time of onset.
Worsening of concurrent diseases or PTEs Worsening of AEs observed in the preceding study	The date on which the subject, the investigator or sub-investigator first noted the first worsening of disease/symptom.
For PTEs: cases in which normal values at the time of screening (i.e., the first test after signing of the informed consent) in the preceding study are abnormal at the subsequent test; For AEs: cases in which abnormal test values are found at the test after the start of administration of the investigational drug	The date on which a clinically abnormal laboratory parameter is observed.

For PTEs: cases in which abnormal test values are found at the first test after signing of the informed consent and they are found to have worsened at the subsequent test; For AEs: cases in which abnormal test values are found at the test after the start of administration of the investigational drug and they worsen at the subsequent test	The date on which a clinically obvious increase/decrease in a laboratory parameter is confirmed based on the time profile of the parameter.
--	---

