## 3.2 Laboratory and Other Safety Data

### 3.2.1 Laboratory Test Results

#### 3.2.1.1 Hematology and Serum Chemistry

Analysis Set: Safety Analysis Set

Analysis Variable(s): Hematology

RBC	Hemoglobin	Hematocrit
WBC		
WBC Differentials (Neutrophil, Eosinophil, Monocyte, Lymphocyte, and Basophil)		
Platelets		
Serum Chemistry		
AST	ALT	γ-GTP
ALP	LDH	Albumin
Total Protein	Total Bilirubin	Total Cholesterol
Triglycerides	Creatinine	
Blood Urea Nitrogen (BUN)		Urine Acid
Creatine Kinase		Sodium
Potassium	Chlorine	Calcium
Phosphorus		

Categories: Results of determination based on reference values  
 [Below lower limit of reference value, Within the range of reference value, Over upper limit of reference value]

Visit:	Baseline (prior to TVP-1012 administration), Week 3, Week 6, Week 14, Week 20, Week 26, Week 29, Week 32, Week 40, Week 46, Week 52
Analysis Method(s):	The following summaries will be provided for each treatment group in the preceding study.
	
 
(1) Descriptive statistics for observed values for each visit and changes (each visit after administration [Week 3 to Week 52] - baseline [prior to TVP-1012 administration]) will be provided.
 
(2) Case Plots
 
(3) A shift table for baseline (prior to TVP-1012 administration) and each visit after administration will be provided for the results of determination based on the reference values.
 

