### **3.2.2.2 12-Lead ECG**

Analysis Set: Safety Analysis Set

Analysis Variable(s): Heart Rate  
RR Interval  
PR Interval  
QT Interval  
QRS Interval  
QTcB Interval  
QTcF Interval

12-Lead ECG Interpretation [Within Normal Limits, Abnormal but Not Clinically Significant, Abnormal and Clinically Significant]

Visit: Baseline (prior to TVP-1012 administration), Week 14, Week 26, Week 40, Week 52

Analysis Method(s): For each variable other than 12-lead ECG interpretations, summaries (1) and (2) will be provided by treatment group in the preceding study.  
For 12-lead ECG interpretation, summary (3) will be provided by treatment group in the preceding study.

- (1) Descriptive statistics for observed values for each visit and changes (each visit after administration (Week 14 to Week 52)-baseline (prior to TVP-1012 administration) will be provided.
- (2) Case Plots
- (3) A shift table for baseline (prior to TVP-1012 administration) and each visit after administration will be provided.

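### The TEAE onset rate by time on drug ignores days at risk, so for events subjects notice between visits a constant hazard is expected to look like a late fall

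*SAP*

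**What the plan says.** Protocol 13.1.4 lists TEAEs over time among the analyses of the primary endpoint. SAP 3.1.2 display (9) implements it by SOC and PT, for each preceding-study group, with these categories: "Time of Onset (days) [1<= - <84, 84<= - <168, 168<= - <252, 252<= - <336, 336<= - <=Max". The numerator is subjects with an onset in the interval. The denominator is "subjects who either have an exposure or have an occurrence of a TEAE, during or after the corresponding time interval". Each such subject counts as one, and the days spent inside the interval do not enter.

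For analyses after TVP-1012, the SAP Glossary takes "the day of first TVP-1012 administration as Day 1". For the placebo-switched group (P→1 mg) that is the first dose in this study. For the group on 1 mg throughout (1 mg→1 mg) it is the first treatment-period dose in the preceding study.

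Protocol 10.1.8 dates events in different ways:
- Signs and symptoms: when the subject or the investigator "first noted the signs/symptoms of an AE".
- Laboratory findings: "The date on which a clinically abnormal laboratory parameter is observed".
- Asymptomatic disease: "The date on which a definitive diagnosis is obtained through tests".

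Laboratory visits after baseline are "Week 3, Week 6, Week 14, Week 20, Week 26, Week 29, Week 32, Week 40, Week 46, Week 52" (SAP 3.2.1.1). ECG visits are "Week 14, Week 26, Week 40, Week 52" (SAP 3.2.2.2).

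SAP 1.3.1 tabulates exposure in the same five bands, but as a separate table that does not feed the rate. Neither document plans a person-time TEAE rate or a footnote on interval length.

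**The concern.** The primary objective is long-term safety, and Protocol 6.2.4 gives the purpose of the extension as safety at 6 and 12 months. Display (9) is the only planned display of TEAEs by time on drug. The 84-day cuts do not match 26 or 52 weeks of treatment, so each group ends with a fragment of an interval that is reported as a percentage beside full intervals.

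The open-ended last category is at least visibly open. The 168 to <252 category is labelled as 84 days, although P→1 mg subjects nominally supply about 15 of them. The same row shows about 84 days for 1 mg→1 mg subjects who continue in the extension. If the percentage drops there, a reader may take it as a decline in risk with continued treatment. A genuine late increase could be flattened in the same way.

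**Working it through.** **1. The plan's own figures.** 26 × 7 = 182 and 52 × 7 = 364. These match the scheduled days for Weeks 26 and 52 in the SAP visit-window tables.

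**2. Length of exposure.** Dosing in the extension starts the day after VISIT 8, and subjects dose on the morning of visits (Protocol 8.1.3).
- P→1 mg, nominal: 364 − 183 + 1 = 182 days.
- P→1 mg, with VISIT 8 on Days 175–189 and VISIT 14 on Days 357–371 (Protocol 9.3.1, 9.3.3): from 357 − 190 + 1 = 168 to 371 − 176 + 1 = 196 days.
- 1 mg→1 mg: 364 days (357 to 371).

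**3. Nominal completer's days in each interval.**

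| Interval | P→1 mg | 1 mg→1 mg |
|---|---|---|
| 1 to <84 | 83 | 83 |
| 84 to <168 | 84 | 84 |
| 168 to <252 | 15 (1–29) | 84 |
| 252 to <336 | – | 84 |
| 336 to Max | – | 29 (22–36) |

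A 1 mg subject who completes the preceding study but does not enter this one also has about 15 days in 168 to <252, and is counted whole.

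**4. What a constant hazard shows, for events noticed between visits.** If p is the risk per 84 days, an interval of d days shows 1 − (1 − p)^(d/84). The documents give no p, so it is ranged.

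| p (assumed) | 15 days | 29 days |
|---|---|---|
| 5% | 0.9% | 1.8% |
| 10% | 1.9% | 3.6% |
| 20% | 3.9% | 7.4% |
| 30% | 6.2% | 11.6% |
| 50% | 11.6% | 21.3% |

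For such events a late hazard increase below 84/15 = 5.6-fold (P→1 mg) or 84/29 = 2.9-fold (1 mg→1 mg) could look flat or falling. For example, a doubling at p = 20% shows 1 − 0.8^(30/84) = 7.7% and 1 − 0.8^(58/84) = 14.3%, both below 20%.

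**5. Events tied to visits.** Here the opportunity to record an onset depends on the schedule. Look-back is the time since the previous visit of that kind, summed over the visits in the interval.

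| Type | Last interval | Interval before |
|---|---|---|
| Signs noted by investigator, P→1 mg | 1 visit, 42 days | 2 visits, 70 days |
| Signs noted by investigator, 1 mg→1 mg | 1 visit, 42 days | 3 visits, 98 days |
| Laboratory, both groups | 1 test, 42 days | 2 tests, 98 days |
| ECG, both groups | 1 test, 84 days | 1 test, 98 days |

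On look-back, masking limits for investigator-noted signs are 70/42 = 1.7-fold and 98/42 = 2.3-fold. If the interval before shows 10%, laboratory-dated events show 1 − 0.9^0.5 = 5.1% by number of tests, or 1 − 0.9^(42/98) = 4.4% by look-back. ECG-dated events show no fall by number of tests and 1 − 0.9^(84/98) = 8.6% by look-back.

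Protocol Appendix A schedules skin examinations only at Weeks 26 and 52. After the first TVP-1012 dose, P→1 mg subjects have one scheduled skin examination, in the last interval. 1 mg→1 mg subjects have none in 252 to <336 and one in 336 to Max. Findings there could rise in the last interval.

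**6. Rare rows.** Take the two intervals as independent binomials with assumed denominators of 91 then 64 (P→1 mg) and 75 then 59 (1 mg→1 mg). The chance of an observed fall is then 56% and 46% at p = 1%, and 95% and 85% at p = 5%.

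**The case against.** A reader might infer that every TEAE dated when first noted will fall in the last interval in proportion to days, that late increases up to 5.6-fold or 2.9-fold are hidden across the board, and that the error is always reassuring. The documents do not support this. Protocol 10.1.8 also covers signs first noted by the investigator, and those follow visits. Laboratory, ECG and skin-examination findings follow their own schedules, and skin findings can move the other way. In a display by SOC and PT, many rows may be too sparse for a fall to show reliably.

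A reader might also infer that the primary safety analysis is biased. It is not: the overview in SAP 3.1.1 and displays (1) to (8) do not use these intervals. Display (9) is descriptive, with no test or decision attached. SAP 1.3.1 lets a careful reader see how far exposure reaches into each band, and SAP 1.1.6 tabulates discontinuations by reason and duration. All of this limits the reach of the point, but none of it corrects the percentage that is printed.

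The strongest objection is to the remedy. Person-time overstates test-dated events in a short interval. Against the interval before, the ECG factor is 84/15 = 5.6 or 84/29 = 2.9, and the laboratory factor is (1/15)/(2/84) = 2.8 or (1/29)/(2/84) = 1.4. That is a good reason to add to the table rather than replace the counts, and to leave SOC-level rates optional.

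**Conclusion.** The concern holds for TEAEs that subjects notice between visits. Under a constant hazard the last interval is expected to show about 18–23% (P→1 mg) or 35–43% (1 mg→1 mg) of the full-interval value, for assumed risks of 5–50% per 84 days. The 168 to <252 row is not comparable between groups for 1 mg subjects who continue, and it is diluted by 1 mg subjects who do not enter.

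The day counts come from the documents. The risk level and the mix of event types are assumptions, so the net effect over all TEAEs cannot be stated. Time of onset is not separately defined. I read it as days from first TVP-1012 dose because the analysis variable is TEAEs after TVP-1012. Counted instead from the start of the preceding study's treatment period, both groups would end with a 29-day interval and the problem would remain.

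This is a correctable weakness in one descriptive table. It deserves correction because that table is the only planned view of TEAEs by time on drug.

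**What to change.** Keep the 84-day cuts, counts and percentages in display (9), and add:
- For each interval and preceding-study group, total person-time at risk, ending at the later of the last TVP-1012 dose and the last AE assessment. For 1 mg subjects who did not enter, use the last AE assessment of the preceding study; its protocol is not among these documents, so that end point must be taken from there.
- A footnote that the last intervals are nominally 15 and 29 days, so their percentages are not comparable with full intervals.
- A footnote that events found at scheduled tests or examinations follow the visit schedule.
- For any TEAE overall, subjects with a first onset in the interval per person-time censored at that onset. SOC-level rates are optional.

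The censoring matters. With constant hazard λ, expected first onsets are 1 − e^(−λd) and expected censored time is (1 − e^(−λd))/λ. The ratio is λ whatever the interval length. Uncensored exposure days do not have this property: at p = 30% they give 0.30/84 × 365.25 × 100 = 130 per 100 patient-years in a full interval and 0.0617/15 × 365.25 × 100 = 150 in a 15-day one.

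The cost is SAP wording and programming for one table, with no new data. The downside is instability. The planned 59 subjects at 52 weeks give 59 × 29/365.25 = 4.7 patient-years in the last interval, so one event is about 21 per 100 patient-years. For P→1 mg no completer number is given. An assumed 64 to 91 (155 − 91 to 182/2) gives 2.6 to 3.7 patient-years, and one event is about 38 to 27. Together with the overstatement of test-dated events, this is why the counts must stay alongside.
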